 - (4) Change in subject specific memory, defined as the MSVT, between baseline and six months post-conversion in both arms
 - (5) Change in subject specific cognitive function, defined as the MoCA, between baseline and six months post-conversion in both arms
 - **(6)** Change in subject specific renal function, defined as the 4 variable MDRD, between baseline and six months post-conversion in both arms

5) Inclusion & Exclusion Criteria

- i) Potentially eligible patients will be screened by the PI and study coordinator using inclusion and exclusion criteria below to determine if they qualify for the study.
- ii) Inclusion criteria
 - (1) Male or female adult (≥18 years old) with a history of liver or liver/kidney transplant within 15 days to 12 months of transplant.
 - (2) Patients must be capable of understanding the purposes and risks of the study and have the ability to give written informed consent and be willing to participate and comply with the study. For those that consent virtually, subjects must be willing and able to use the Doxy.me platform and complete assessments virtually.
- iii) Exclusion criteria
 - (1) Patients will be excluded if they are pregnant or nursing females or males with a pregnant female partner
 - (2) HIV positive (HIV ab +)
 - (3) Unable to tolerate oral medications
 - (4) Use of another investigational product within thirty days prior to receiving study medication
 - (5) Moderate acute cellular rejection (RAI ≥ 5) within the past month
 - **(6)** A condition that is known to cause tremor such as essential tremor, Parkinson disease, or enhanced physiologic tremor.
 - (7) Patients taking medications known to induce tremors or dopamine blocking agents

(8) A condition or disorder that, in the opinion of the investigator, may adversely affect the outcome of the study or the safety of the subject

6) Number of Subjects

a) There will be 15 subjects in each arm, 30 subjects total

7) Setting Where Research Will Be Conducted

a) Study activities, including consent, enrollment, and randomization, will occur in the Liver Transplant Clinic at the Medical University of South Carolina or through Doxy.me.

8) Recruitment Methods

- a) Study enrollment procedures

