 - i) Subject Identification/Recruitment: Members of the research team will identify potentially eligible patients who have undergone liver or liver/kidney transplantation within the past twelve months. An initial evaluation of existing patient information may be performed via chart review to determine potential eligibility. This initial review may be performed prior to consent; however no protocol driven tests or procedures may be performed until signed informed consent has been obtained.
 - ii) Informed Consent: A qualified member of the research team, Human Subjects Protection Trained, will approach and explain the study and offer participation. The study will be explained in a manner consistent with the level of education pertaining to the patient. Enrollment procedure will involve face-to-face meetings of the patients to inform and review informed consent documentation. The participant will sign the consent form prior to evaluation of self-reported measures. Copies of the informed consent will be appropriately placed in the corresponding chart and the patient will be provided with a copy of the signed consent form. Non-consenting individuals will also be ensured that no penalty will arise due to denying participation. Those who choose to participate in the trial will be informed that at any point they reserve the right to leave the study.
 - iii) Enrollment: Patients who give informed consent to study participation will go on to complete baseline procedures necessary to determine eligibility for randomization. Once deemed eligible for the study according to the inclusion/exclusion criteria, the patient will be enrolled as study participant. Information to be entered upon enrollment includes demographic information and date of transplant surgery. Enrolled subjects will be randomized to one of the treatment arms in the applicable cohort.

9) Consent Process

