 - (1) No deviations from or changes to the study protocol should be initiated except when necessary to eliminate immediate hazard to the subject. However, the IRB and Study Sponsor must be informed of this as soon as possible thereafter. It is the PI's responsibility to report SAEs occurring during the study to the IRB, as required and as soon as possible.

10) Study design

- i) Single-center, open-label, randomized comparative trial for a duration of 6 months.
- ii) There will be 15 subjects in each arm, with a total study size of 30 subjects.
- **b)** Allocation: Three random permuted-blocks of ten, with equal arm allocation ratio will be used. In each block, REDCap will be used to ensure 1:1 randomization, with resulting 1:1 allocation in the overall cohort.
- c) Intervention Model: Parallel assignment
- **d)** Masking: This will be an open-label study as masking is not feasible given we are comparing twice-a-day to once-a-day regimen.
- e) Timing of evaluation
 - i) Pre-Randomization Evaluations
 - 1. Baseline
 - Evaluations listed under the baseline visit may be performed up to 14 days prior to randomization. Once the subject has been successfully screened and accepted for randomization, randomization must be completed within 48 hours.
 - ii) Intervention and Evaluations
 - Once the subject has been successfully randomized, study medication will be picked up from IDS by the study team to be dispensed to the subject or study medication will be shipped to the subject by IDS. Study evaluations must take place within the time window indicated on the Schedule of Evaluations (Section 3)
- f) Clinical and laboratory evaluations

i) Schedule of evaluations

Data Collection Schedule

	Baseline	Baseline Days Post-Conversi					on			
Report Form			7±2	14±3	30±5	60±7	90±10	120±10	150±10	180±10
Informed Consen	t Obtained ^{vi}	Х								
Randomization		Х								
Review of Inclusion	on and Exclusion Criteria	Х								
Medical History		Х								
Liver Transplant F	Recipient	Х								
Review of Medica	ations and Dosing	Х								Х
Clinical assessment* Adverse events, rejection, graft loss, death						х			х	
	PGI-I, IMAB-Q 10, MSVT, MoCA, and SF- 12, MMSE ^v	х								х
	Fahn-Tolosa-Marin ^{iv}	Х								Х
Laboratory	CBC and Chem-7 ⁱ	0	0	0	0	0	0	0	0	0
Assessments	LFTs ⁱⁱ	0	0	0	0	0	0	0	0	0
	Tacrolimus CO ⁱⁱⁱ	0	0	0	0	0	0	0	0	0
End of Study										Х

X=required; 0=optional: data will be collected if performed as standard of care Footnotes:

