 - (1) Opportunistic infections will be defined as outlined in Appendix F
- v) Intervention Discontinuation Evaluations: At the scheduled time of intervention discontinuation (EOT, last date of study), the following evaluations must be completed: clinical assessment, CBC, CHEM-7, LFTs, Tacrolimus CO. In case of subject withdrawal from study, the patient will return to standard of care medications and request to continue with final assessment using PGI-I, IMAB-Q 10, MSVT, MoCA, SF-12, MMSE, and FTM (if applicable) will be discussed with a qualified team member.

12) Data Management

- a) Data management will be overseen and data analysis will be independently reviewed by an Investigator on the study who has no related financial interest. This member will serve as independent monitor to oversee data collection and management, and to verify the integrity of data and interpretation of study results. Data reports, including patient recruitment and randomization numbers, clinical outcomes (acute rejections, infections and hospitalizations), AEs and SAEs will be reviewed quarterly.
- b) Dichotomous data will be analyzed using Chi Square or Fischer Exact, when appropriate, and continuous data points will be analyzed using Student's t-test or Mann Whitney U, for parametric and nonparametric data, respectively.
- c) Sample size estimation for the primary outcome
 - i) The proposed sample size (n=30) would be able to demonstrate a mean difference in neurologic toxicity burden, using the Patient Global Impression of Improvement (PGI-I) rating of 20 ± 15 with greater than 80% power using a two-tailed t-test with an alpha set at 0.05. Based on reported neurologic toxicities from the literature (headache 64%, insomnia 64%, tremor 56%, paresthesia 40%), a mean score of 45 is expected at baseline. Using the independent samples t-test comparing two groups with a two-sided significance level of

0.05, a sample size of 14 subjects per group would be required to obtain a power of at least 0.8 if the two groups have a mean of 25 ± 15 neurologic toxicity burden in the Envarsus cohort at the conclusion of the study and mean of 45 ± 20 neurologic toxicity burden at baseline and follow up in the tacrolimus IR group. Estimating a 10% drop out rate, we propose a sample size of 15 subjects per group. This sample size will provide adequate power to show a statistical and clinical difference in the neurologic toxicity burden between the two groups.

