Appendix F: SF-12

In general, would you say your health is: * must provide value					
Excellent Very good Good					
O Fair O Poor					reset
The following questions are about activitie these activities? If so, how much?	s you might do	during a typical	day. Does YOUR H	IEALTH NOW L	
	Yes, limited	a lot	Yes, limited a little	No, no	t limited at all
Moderate activities, such as moving a table, pushing a vacuum cleaner, bowling, or playing golf * must provide value	0		0		0
Climbing SEVERAL flights of stairs * must provide value	0		0		reset
During the PAST 4 WEEKS, how much of the regular daily activities AS A RESULT OF YOU	-	-	ollowing problem	s with your wo	rk or other
	All of the time	Most of the time	Some of the time	A little of the time	None of the time
ACCOMPLISHED LESS than you would like * must provide value	0	0	0	0	0
Were limited in the KIND of work or other activities * must provide value	0	0	0	0	reset
During the PAST 4 WEEKS, how much of the regular daily activities AS A RESULT OF ANY	_	-		-	
	All of the time	Most of the time	Some of the time	A little of the time	None of the time
ACCOMPLISHED LESS than you would like * must provide value	0	0	0	0	0
Did work or other activities LESS					reset

During the PAST 4 WEEKS, how much did P and housework)?	AIN interfere wi	ith your normal v	work (including b	oth work outsi	reset ide the home
* must provide value Not at all A little bit Moderately Quite a bit Extremely					
These questions are about how you feel a question, please give the one answer that the PAST 4 WEEKS	_				
	All of the time	Most of the time	Some of the time	A little of the time	None of the time
Have you felt calm and peaceful? * must provide value	0	0	0	0	0
Did you have a lot of energy? * must provide value	0	0	0	0	reset
Have you felt downhearted and depressed? * must provide value	0	0	0	0	reset
During the PAST 4 WEEKS, how much of th your social activities (like visiting with frie	-		'H OR EMOTIONA	L PROBLEMS in	reset sterfered with
• must provide value All of the time Most of the time Some of the time A little of the time None of the time					

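### Entry ranges from 15 days to 12 months after transplant, yet neither randomisation nor analysis uses time since transplant, which costs precision and leaves chance imbalance unadjusted in arms of 15

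*Combined protocol and SAP*

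**What the plan says.** - **Entry (Section 5, inclusion criterion 1).** "Male or female adult (≥18 years old) with a history of liver or liver/kidney transplant within 15 days to 12 months of transplant".
- **Allocation (Section 10b).** "Three random permuted-blocks of ten, with equal arm allocation ratio will be used", and "REDCap will be used to ensure 1:1 randomization, with resulting 1:1 allocation in the overall cohort". No stratification factor is named. Section 10a gives the size: "There will be 15 subjects in each arm, with a total study size of 30 subjects".
- **Analysis (Section 12b).** Student's t-test or Mann-Whitney U for continuous data. No covariate is named there or elsewhere.
- **Data available (Sections 8a and 9b).** "Information to be entered upon enrollment includes demographic information and date of transplant surgery". The date has no later role in the design or the analysis.
- **Primary instrument (Appendix B).** Each of the four PGI-I items asks the patient to compare the symptom now with its state before the transplant.
- **Sample size (Section 12c).** 25 ± 15 in the Envarsus arm at the end of the study, against a "mean of 45 ± 20 neurologic toxicity burden at baseline and follow up in the tacrolimus IR group".
- **SF-12 (Appendix F).** Most items refer to the past four weeks.

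**The concern.** One patient may be followed from about two weeks after surgery through the first six months of recovery, and another from month 12 to month 18. If six-month change depends on where in that course a patient starts, time since transplant is a prognostic factor. The primary instrument makes this plausible: at baseline one patient looks back about two weeks to the reference point and another about a year.

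Permuted blocks equalise arm numbers and balance calendar time. They do not balance time since transplant. With 15 per arm, one arm can by chance hold clearly more early entrants, and an unadjusted test leaves that difference in the estimate. Even when the arms are balanced, the variation due to entry time stays in the error term. At stake is the precision of the primary comparison and of the other continuous change outcomes. Rejection, graft loss, death and adverse events are not change scores and are outside this point.

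**Working it through.** **1. The plan's own sample size.** Inputs from Section 12c: means 25 and 45, SDs 15 and 20, two-sided alpha 0.05.

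- Root-mean-square SD = √((15² + 20²)/2) = √312.5 = 17.68.
- Noncentral t power: 0.790 at 13 per arm, 0.822 at 14, 0.849 at 15. The stated 14 per group is reproduced.
- Smallest significant difference at 15 per arm = t(0.975; 28 df) × 17.68 × √(2/15) ≈ 13.2 points.

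**2. How far apart the arms can be at entry.** Assumption: entry uniform over days 15 to 365. The documents give no distribution.

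- SD of entry time = 350/√12 = 101 days.
- SD of the between-arm difference in means = 101 × √(2/15) = 37 days.
- P(gap > 60 days) ≈ 0.10 by simulation. In a separate run with the three blocks of ten and entry over 0.5 to 12 months, P(gap > 2 months) was also 0.10.
- P(gap > 0.5 SD, about 50 days) = 2 × [1 − Φ(0.5/√(2/15))] = 0.17.
- If instead 10 of 30 patients are early entrants (assumption), a split of 7:3 or worse, in either direction, has probability 0.245.

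**3. What such a gap does to the result.** Let ρ be the correlation between time since transplant and the outcome. The documents give no value, so a range is shown. They also give no SD for change, so 17.68 is used. The shift from a 0.5 SD gap is ρ × 17.68 × 0.5. The other columns come from 200,000 simulated trials with 15 per arm; the two power columns take a true difference of 20.

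| ρ | Shift (points) | False-positive rate of t-test, given gap > 0.5 SD | Power when a gap > 0.5 SD goes against Envarsus: t-test → adjusted | Power over all trials: t-test → adjusted |
|---|---|---|---|---|
| 0.2 | 1.8 | 6% | 0.75 → 0.81 | 0.85 → 0.85 |
| 0.3 | 2.7 | 7% | 0.70 → 0.84 | 0.85 → 0.87 |
| 0.5 | 4.4 | 12% | 0.57 → 0.89 | 0.85 → 0.92 |
| 0.7 | 6.2 | 18% | 0.41 → 0.97 | 0.85 → 0.98 |

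The adjusted analysis is ANCOVA with time since transplant as the only covariate. Over all randomisations the unadjusted t-test keeps its false-positive rate at 5%. ANCOVA keeps about 5% in the imbalanced trials as well.

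**4. SF-12 recall.** A four-week recall reaches back before the transplant for any baseline taken before day 28. Under uniform entry that is (28 − 15)/(365 − 15) = 13/350 = 3.7% of patients, or 0.037 × 30 ≈ 1 patient. The number is higher if patients are enrolled as soon as they qualify.

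**The case against.** The control arm is randomised and concurrent. Recovery therefore falls equally on both arms on average, and the standard error of the t-test already allows for chance imbalance. This stands. A reader might infer that post-transplant recovery could pass for a drug effect. The documents do not support that: there is no systematic bias, overall type I error is 5%, and a 0.5 SD gap moves the result by about 2 to 6 points where about 13 are needed for significance. Such a gap can distort an estimate or help hide an effect, but would not by itself produce a significant result.

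A reader might also infer that the flat control mean in Section 12c invalidates the sample size. It does not. Power rests on 45 against 25 at follow-up, and equal recovery in both arms leaves that 20-point contrast intact. Section 2 also notes that milder neurotoxicity can persist.

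The size depends on an undocumented correlation. This stands too: at 0.3 or below the harm is modest, and at 0.2 adjustment leaves power at 0.85. But the covariate is already collected and costs almost nothing, so uncertainty about the gain is a weak reason to leave it out.

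The SF-12 issue is small: an exploratory questionnaire and about one patient in 30 under uniform entry. It does not justify changing when patients may enter.

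**Conclusion.** The point holds as one of precision and chance imbalance. The plan admits patients across most of the first post-transplant year, records the transplant date, and then uses it in neither allocation nor analysis. Under uniform entry, about one trial in six would have a gap above 0.5 SD. How much that matters ranges from little (correlation 0.2) to material (0.5 or more), and the documents do not show where the trial lies. The uniform entry pattern, the correlation range and the use of 17.68 as outcome SD are all assumptions. The plan should be changed because the remedy is cheap, not because the primary comparison is biased.

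**What to change.** **Main change.** In Section 12b, prespecify ANCOVA for the primary outcome and the other continuous change outcomes, with baseline score and time since transplant (days from transplant to randomisation) as covariates. The cost is one degree of freedom per covariate: 30 − 2 = 28 residual degrees of freedom become 26 with two covariates. If the correlation is low, little is gained. This works even if enrolment has begun.

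**Optional, if randomisation is still open.** Add one early/late stratum. Three blocks of ten cannot be kept across two strata, so blocks must be smaller and the final split may depart slightly from 15:15. In an open-label, single-centre trial small blocks are also easier to predict, which is a further reason to treat adjustment as the main remedy.

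**SF-12.** Add a sensitivity analysis of SF-12 change without baselines taken before day 28. Keep all patients in the main analysis, in line with the intention-to-treat statement in Section 12d, and do not delay enrolment for this purpose.

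**Wording.** Section 3a(i) treats 15 days as an upper limit on prior standard of care, while Section 5 treats day 15 as the earliest entry. The two must be reconciled. The text should also say at which step the window is counted, since Section 10e allows baseline assessments up to 14 days before randomisation.

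### A fixed block size of ten, printed in the protocol of a single-centre open-label trial, would let a team member who keeps a tally predict an expected 5 of 30 allocations with certainty

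*Combined protocol and SAP*

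**What the plan says.** Section 10 b) sets the allocation scheme: "Three random permuted-blocks of ten, with equal arm allocation ratio will be used". It continues: "In each block, REDCap will be used to ensure 1:1 randomization, with resulting 1:1 allocation in the overall cohort". Three blocks of ten use up all 30 places, and section 10 confirms the total: "There will be 15 subjects in each arm, with a total study size of 30 subjects". No stratification factor is described.

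The design is given as "Single-center, open-label, randomized comparative trial for a duration of 6 months", and section 10 d) explains the lack of masking: "This will be an open-label study as masking is not feasible given we are comparing twice-a-day to once-a-day regimen".

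On who enrols, section 5 says "Potentially eligible patients will be screened by the PI and study coordinator using inclusion and exclusion criteria below". Section 7 says "Study activities, including consent, enrollment, and randomization, will occur in the Liver Transplant Clinic", or by the telemedicine platform. Under section 10 e) the study team may collect the study drug from the pharmacy service and hand it to the patient.

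The protocol does not say that block sizes vary, that the size is withheld from recruiters, or who prepares and holds the list.

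**The concern.** REDCap can hide the next entry in the list. It cannot hide an allocation that follows from a known block size and a visible history. With one site, no masking, no stratification and a fixed size of ten, a single running count is enough.

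The protocol also leaves room to act on such knowledge. Charts may be reviewed before consent (section 8), so likely prognosis is visible before a patient is approached. Entry is open from 15 days to 12 months after transplant, and one exclusion rests on the investigator's opinion (section 5).

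At stake is the comparability of two arms of 15 on a patient-completed composite. Section 12 b) plans a t-test or Mann-Whitney test, with no covariate adjustment and no check for selection.

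**Working it through.** **Inputs.** From section 10: three blocks of ten, 1:1, N = 30. From section 12 c): means 25 and 45, SDs 15 and 20, two-sided alpha 0.05, 14 per group for power of at least 0.8, raised to 15.

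**The plan's own figures.** Pooled SD = √((15² + 20²)/2) = 17.68. For a difference of 20, the noncentral t gives power 0.790 at 13 per group and 0.822 at 14, so 14 reproduces. 3 × 10 = 30, or 15 per arm, also agrees. The plan gives no figure for predictability.

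**Certain allocations per block.** A block of ten has C(10,5) = 252 equally likely sequences. The certain allocations are the final run of identical assignments after the other arm is full. The probability of exactly k is 2 × C(9−k, 4)/252:

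| k | Sequences | Probability |
|---|---|---|
| 1 | 140 | 0.556 |
| 2 | 70 | 0.278 |
| 3 | 30 | 0.119 |
| 4 | 10 | 0.040 |
| 5 | 2 | 0.008 |

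Mean = (140 + 140 + 90 + 40 + 10)/252 = 420/252 = 1.667. This matches the closed form 2m/(m+1) with m = 5.

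**Whole trial.** 3 × 1.667 = 5.0 of 30, or 16.7%. The minimum is 3 (patients 10, 20 and 30) and the maximum 15. About 93% of sequences give 3 to 7, and P(at least 5) = 0.571.

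**Best guesses.** Always guessing the arm that is behind is right 5 + (4⁵/252 − 1)/2 = 6.53 times per block. That is 19.6 of 30 (65%), against 15 by chance.

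**Illustration of consequence.** The assumption is that patients placed at certain slots differ from the rest by η points in expected change, favourably in one arm and unfavourably in the other, at every such slot. On average 2.5 certain slots fall in each arm, so each arm mean moves by 2.5η/15 and the bias is 2η × 5/30. SE = 17.68 × √(2/15) = 6.45. The SD comes from the plan's scores and stands in for the SD of change, which the plan does not give. Type I error is from the noncentral t on 28 df with noncentrality bias/SE.

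| η (assumed) | Bias | Noncentrality | Type I error |
|---|---|---|---|
| 2.5 | 0.83 | 0.13 | 0.052 |
| 5 | 1.67 | 0.26 | 0.057 |
| 10 | 3.33 | 0.52 | 0.079 |

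If staff acted on every best guess with η = 5, the bias would be 2 × 5 × (2 × 19.6 − 30)/30 = 3.1 points and the type I error 0.074.

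**Alternatives.** These were simulated with an observer who knows the set of sizes but not their order:

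| Scheme | Certain of 30 | Best guess right, of 30 |
|---|---|---|
| Fixed 10 | 5.0 | 19.6 |
| 6, 8, 10 drawn at random, cut at 30 | about 0.5 | 19.7 |
| 6, 8, 10 totalling exactly 30 (18 orderings, equally weighted) | about 2.2 | 20.1 |

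Smaller fixed blocks, if known, would be worse: 25% of allocations are certain with size 6 and 33% with size 4.

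**The case against.** Several points on the other side stand.

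- **The deduction is conditional.** A reader might infer that the team knew these allocations, or that the block size was public during enrolment. The documents show only that the size is printed in the protocol. They do not show that anyone kept a tally, or that selection took place. Five is an average, not a count.
- **There is a partial safeguard.** Section 10 e) requires randomisation within 48 hours once a patient has been accepted. That limits holding back an accepted patient. Steering would have to come earlier, in whom to approach or when to screen.
- **The analysis is not powerless.** A reader might infer that it can neither detect nor remove the bias. Section 4 defines the primary outcome as change from baseline, and the schedule in section 10 f) puts the baseline composite before randomisation. Selection on current burden would tend to show as a baseline imbalance and be partly differenced out. Selection on expected trajectory, for instance through time since transplant, would not, and the planned unadjusted test does not address it.
- **The larger illustrative figure is not what the fix prevents.** The 0.074 comes from acting on best guesses, and varying block sizes leave those as accurate as before. Only the certain-slot scenario improves.
- **Ten is already a fairly large block** for a trial of 30.

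These points limit the severity. They do not remove the opening, because nothing in the protocol varies or withholds the block size.

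**Conclusion.** The point holds as a weakness in allocation concealment. The exact expectation of 5.0 certain allocations in 30 rests on two conditions that the documents permit and do not exclude: the person enrolling knows the block size, and keeps a count.

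The resulting bias cannot be derived from the documents. For an assumed and consistently exploited difference of 2.5 to 10 points, the illustrated type I error runs from 0.052 to 0.079, and the bias scales in proportion to the assumption. These figures carry the whole difference into change from baseline, so for selection on baseline burden alone they are too high.

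This is a cheap improvement of minor to moderate severity. It is not evidence that the comparison is compromised.

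**What to change.** Load into REDCap a list of permuted blocks whose sizes are drawn at random, for example from 6, 8 and 10. Cut the list at 30 and allow it to end inside a block. Have it prepared by someone who does not enrol patients. Replace the allocation sentence in section 10 b) with: *permuted blocks of varying size, not disclosed to the enrolling team*. Relax the exact 15-per-arm wording in sections 6 and 10 to match. If exactly 15:15 must be kept, blocks totalling 30 still cut the certain allocations from 5.0 to about 2.2.

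If enrolment has begun, apply the new list to the remaining slots. If it is complete, report the fixed block size as a limitation and compare the baseline features of patients enrolled at the forced positions with those of the rest.

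The cost is one allocation table and a few words of text, with no change to total sample size, visits or treatment. The downside is a possible slight departure from 15:15. With these sizes the unfinished block holds an even number of patients and can be unbalanced by at most 4, so the worst split is 17:13. At a common SD that raises the standard error by a factor of √(1/17 + 1/13)/√(2/15) = 0.368/0.365, or about 1%.
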